(3) The patient has not informed study staff or the psychiatric clinician of any condition that, in the opinion of the PI or PI's designee, would make the patient unsuitable for or unable to complete further screening

Following the in-person screening visits and Pre-Baseline data collection, the patient will undergo the Baseline visit including MRI scan and randomization. At the Baseline visit, urine will be obtained for toxicology and pregnancy testing (where appropriate) and a fMRI scan will be performed. Subjects will receive standardized clinician-administered interviews and ratings for psychiatric symptoms, will be asked to fill out self-report questionnaires and will undergo objective tests of motivation and motor activity. Blood will also be drawn for the measurement of inflammatory marker/hormone levels after the scan procedures, and patients will receive study medication. At the end of each indicated week of treatment (7 days after each dose change in weeks 1, 3, 4 and 6), subjects will undergo fMRI scans, receive standardized clinician-administered interviews and ratings for psychiatric symptoms, will be asked to fill out self-report questionnaires, have blood drawn for L-DOPA concentrations and inflammatory markers, urine will be obtained for toxicology, and pregnancy testing, and will perform objective tests of motivation/motor activity. Safety and tolerability will also be assessed. For follow up visits at weeks 2 and 5, patients will either be seen in person (where possible) or virtually to fill out self-report questionnaires, height, weight and vital signs will be recorded (in-person only), update psychiatric symptoms, and safety and tolerability will be assessed. If the visit occurs virtually, medication will be mailed to the participant and unused medication will be returned at the next in-person visit.

Table 2. Schedule of Study Procedures and Assessments.

| Assessments | Intake/ Consent | Screen A | Screen B- (Incl. Pre- Baseline Assess.) | Baseline | Weeks 1, 3, 4, 6 | Weeks 2 & 5 |
|--|--------------------|----------|--|----------|---------------------|----------------|
| Consent, Intake Registration Form, PHQ-9 [Intake or Screen A, optional at Screen B], Med-Psych Prescreen Form, History of Chronic Conditions, Medication Avoidance List* | X | [X] | [X] | | | |
| SCID V-modified (Mood, Anxiety, PTSD modules), Bipolarity index, ATRQ, Clinical Review for Screening** | X | [X] | [X] | | | |

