| C-reactive protein (CRP), Rapid CRP Finger Prick [if necessary to verify CRP]* | | X | [X] | [X] | | |
| MRI Safety Screening, Anti-nuclear AB, TSH, Serum Pregnancy (hCG), Hepatitis B surface antigen, Hepatitis C antibody, HIV antigen/antibody* | | X | [X] | | | |
| EKG | | X | [X] | | | |
| Urine pregnancy test* | | | [X] | X | X | [X] |
| Physical Exam | | | X | | | |

| Adverse Events, Concomitant Medications* | X | X | X | X | X | X |
|---|---|---|-----|---|---|-----|
| Vital Signs, weight, height [screen only], waist-hip ratio [screen only] | | X | X | X | X | [X] |
| CBC with differential, urinalysis w/ micro, comprehensive metabolic panel* | | X | [X] | | | |
| Urine toxicology | | X | [X] | X | X | [X] |
| Demographic Data, Habits, CTQ, IDS-SR | | | X | | | |
| Randomization (Track A or Track B) | | | X | | | |
| Study Medication Dispensing, Dose Change and/or Compliance Check | | | | X | X | X |
| Research Blood (fasting) | | | X | | | |
| Research Blood (Non-Fasting) | | | | X | X | |
| HAM-D item #3, Columbia Suicide Severity Rating Scale (CSSRS), Clinical Review for Follow Up, Dyskinesia Symptom Review | | | | X | X | X |
| Psychiatric Assessments (HAM-D, SHAPS-C), HAM-A [Baseline only, optional for all other visits]*** | | | | X | X | X |
| Self-Report Forms (IDS-SR/IDS-Anhedonia, MAPS-SR, BAI, STAI, PSS, PCL-5, Habits) | | | | X | X | X |
| EEfRT (Motivation), Neurocognitive Testing | | | X | X | X | |
| MRI Scan | | | | X | X | |

*These assessments may be conducted in the Emory behavioral Immunology Program research screening clinic

** A Clinical Review will be conducted if more than 2 weeks from last assessment or as an update to SCID modules conducted in the Behavioral Immunology Program within the past 6 months

***HAM-A removed from Baseline visit on 7/11/22.

[] to be completed if needed

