DOPA will have in depression, and risks are assumed to be small, procedures will be put in place to ensure that any risks associated with receiving L-DOPA are minimized. At screening, subjects will be carefully evaluated for the presence of any medical conditions that might increase the risk of an adverse events (for example cardiovascular issues uncovered by EKG). Subjects will be evaluated by medical personnel weekly during treatment and will be available 24/7 if problems arise. All procedures will be conducted in the Emory University Hospital facilities where emergency assistance will be available if needed. Between signing consent and completing the screening assessment, a period of no more than 2 weeks will pass until baseline, and during this period either the patient will be taken off-study, or a study clinician or their designee will contact and evaluate the subject every 7 days to ensure that symptoms haven't worsened appreciably or that suicidal ideation has not developed. In the case of either of these eventualities, subjects will be discontinued from the study immediately and appropriate psychiatric referral will be made. Specific indications for discontinuation between screening and baseline will include any of the following: 1) the development of suicidal ideation or attempt assessed by spontaneous subject report or by scoring >3 on the HAM-D suicide item [item #3] at any assessment or 2) the development of psychotic or catatonic symptoms at any assessment. Other criteria for discontinuation between screening and the baseline visit include: hospitalization for any reason or a clinical judgment that a subject is an imminent threat to self or others. Subjects will be evaluated for the appropriate level of care, including emergency hospitalization if indicated. Subjects with non-emergent symptoms but who disqualify for further participation will be referred back to their primary psychiatric physician. Appropriate follow-up care will be arranged for subjects not in active psychiatric treatment. An individualized plan will be crafted for each subject to ensure psychiatric back-up should emergency psychiatric care be required after hours or on weekends. Upon completion of the study protocol, all depressed subjects without a current psychiatrist will be offered an appropriate referral.

Confidentiality and Data Management:

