Appointment Scheduling & Reminders: All participants will be given the opportunity to receive appointment reminders and scheduling information via text message on their mobile phones. If the subject consents to this form of communication, study staff may use OhMD Texting Service to communicate with participants. This platform provides a Desktop and Mobile Version of OhMD for the research team to securely communicate with participants and maintain subject confidentiality. This service will only be used for communicating relevant appointment information and never used for PHI. Participants will receive the following text message from the study team upon first contact: "Please do NOT send any personal information via text. You may call the study team at [contact] to discuss any personal or health details." Any PHI received via text message will be reported to the IRB as a potential breach of confidentiality

Stopping Rules:

Subjects will be closely evaluated throughout the study for worsening of psychiatric symptoms. Subjects will be discontinued at any point for any of the following: 1) the development of significant suicidal ideation, plan or intent as determined by spontaneous subject report or as determined by scoring >3 on the HAM-D suicide item [item #3], 2) the development of psychotic or catatonic symptoms, or 3) a 25% increase from baseline of HAM-D score, 4) below 85% compliance on more than one week during the study, and 5) positive pregnancy test. Subjects requiring discontinuation will be referred for further evaluation and treatment by one of the study psychiatrists. All unanticipated and/or serious adverse events or problems will be reported to the DSMB, IRB and NIH and we will follow their recommendations for stopping the overall study.

6.4 Research material will be derived from clinician-administered and self-report questionnaires, blood, urine, objective behavioral tests and fMRI scans. Material for evaluating baseline medical status and subject safety prior to randomization will be obtained from blood and urine. Data to be recorded from subjects will include standardized ratings of emotional, cognitive and physical symptoms, as well as clinical information derived from medical records when available, interviews with the subject, referring physicians and family members when relevant. Data will be obtained from peripheral blood, including complete metabolic panel, CBC with differential,

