14.0 Withdrawal of Participants*

- 14.1 Patients may be drawn from the research without their consent if they experience a severe adverse event thought to be attributed to the study procedures, due to repeat non-compliance with study procedures (2 or more of the same violation), worsening of depressive symptoms including suicidal ideation, or for any other reason that the PI or Study Physicians determine to be putting the participant at increased risk or jeopardizing integrity of the study data.
- 14.2 To withdraw a participant, the study team will contact the subject to inform them that they should discontinue use of all study medication and to schedule a follow-up visit for the participant to be assessed by study clinicians for medical and psychiatric safety. The participant will be asked to return all unused medication at this time, and a member of the study team will take them off study. If the patient is determined to be a potential risk to themselves or others on the call or in the final interview, Drs. [name] or [name] will be immediately contacted, and an appropriate clinical intervention plan will be developed.
- 14.3 When participants withdraw from this study, they will be appropriately off-studied and their participation will be terminated. Because this study is a mechanistic study to demonstrate target engagement using a within-in subject design, no partial withdrawal with continued data collection will be allowed for participants who miss their scheduled MRI, blood and neurocognitive follow-up assessments.

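### The mandatory on-study suicidality rule names neither the C-SSRS nor clinical judgment of imminent risk, so plan or intent elicited by questioning does not itself compel discontinuation

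*Combined protocol and SAP*

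**What the plan says.** The on-study rule is in Section 6.3 under Stopping Rules and is mandatory: "Subjects will be discontinued at any point for any of the following". Its first criterion is "the development of significant suicidal ideation, plan or intent as determined by spontaneous subject report or as determined by scoring >3"; the score meant is that of HAM-D item #3, which rates suicidality. The other four are psychotic or catatonic symptoms, a 25% rise in HAM-D score from baseline, compliance under 85% in more than one week, and a positive pregnancy test.

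Table 2 (Section 6.1) has one row that begins "HAM-D item #3, Columbia Suicide Severity Rating Scale (CSSRS), Clinical Review for Follow Up". It is marked at Baseline, at Weeks 1, 3, 4 and 6, and at Weeks 2 and 5. This row is the only mention of the C-SSRS in the text supplied. No threshold or action is attached to it.

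Section 14.1 covers withdrawal at the study team's initiative and is permissive: "Patients may be drawn from the research without their consent". The reasons include "worsening of depressive symptoms including suicidal ideation", and anything else that the investigator or study physicians think puts the participant at increased risk.

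Between screening and Baseline a different text applies (Section 6.3, L-DOPA Treatment). Either the patient is taken off study or "a study clinician or their designee will contact and evaluate the subject every 7 days", and new suicidal ideation leads to immediate discontinuation. The specific indications listed there use the same two routes, spontaneous report or item #3 above 3. A further criterion is a clinician's judgment that the person is an imminent danger to self or others.

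**The concern.** The first stopping criterion is written for ideation, plan or intent, but it limits how these may be established. An answer given to a C-SSRS question, or to a clinician's direct question, is elicited rather than spontaneous. Unless it also moves item #3 above 3, it does not meet the criterion as worded. The dedicated suicidality scale is collected at every visit from Baseline onward and feeds no mandatory rule.

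Exclusion f (Section 10.2) bars only an active suicidal plan, so depressed, medication-free patients with ideation but no plan can enter. Progression from ideation to plan or intent during treatment is the event that the criterion is there to catch. Visits at Weeks 2 and 5 may be virtual (Section 6.1), where an unambiguous written rule is most useful. What is at stake is whether such a finding must lead to discontinuation, or whether that is left to whoever is on duty.

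**Working it through.** No figure in the plan bears on whether the rule is adequate, so the check sets the provisions side by side.

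| Source of information | Between screening and Baseline (6.3, L-DOPA Treatment) | On study (6.3, Stopping Rules) | On study (14.1) |
|---|---|---|---|
| Spontaneous report | Mandatory | Mandatory | Permitted |
| HAM-D item #3 above 3 | Mandatory | Mandatory | Permitted |
| C-SSRS | Not named | Not named | Not named; could be acted on |
| Clinician judges imminent danger | Listed criterion | Not listed | Permitted, as increased risk |
| 25% rise in HAM-D total | Not listed | Mandatory | Permitted, as worsening |

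Now take a participant who, at any weekly visit, first discloses a plan or intent in answer to the C-SSRS or an interview question.

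1. If item #3 is scored above 3 at that visit, discontinuation is mandatory through item #3.
2. If item #3 is 3 or below but the HAM-D total is at least 25% above baseline, discontinuation is mandatory through the third criterion.
3. If neither holds and the participant volunteered nothing, no mandatory criterion is met. Section 14.1 allows withdrawal but does not require it.

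In none of the three cases does the C-SSRS answer itself decide the outcome. The gap is case 3. The documents give scoring anchors for neither scale, so they do not show how often case 3 would arise, or whether it would arise at all.

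The only arithmetic concerns the cost of tightening the rule. The allowance for losses is 35 − 30 = 5 participants, or 5/35 = 14.3% of those randomized (Section 12.2). The expected attrition of about 10–15% corresponds to 0.10 × 35 = 3.5 up to 0.15 × 35 = 5.25 participants, so the allowance roughly equals the losses already expected. Section 14.3 adds that "no partial withdrawal with continued data collection will be allowed for participants who miss their scheduled MRI" or the other follow-up assessments, so each discontinuation ends that participant's data collection.

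**The case against.** The strongest reply is that the criterion already has a clinician-elicited route. The HAM-D is clinician-administered (Section 6.2), and item #3 is in the same Table 2 row as the C-SSRS, so it is rated at the same visits. That stands. A reader might infer that nothing elicited by a clinician can trigger discontinuation on study, and that would be wrong. The point is narrower: a second, dedicated instrument is collected and not used.

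The contrast with the pre-Baseline text also needs care. Its specific indications use the same two routes and do not name the C-SSRS either. The clear differences are the immediate discontinuation for new ideation found at the 7-day evaluations and the imminent-danger criterion. Neither was carried into the on-study list.

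Other safeguards remain: close evaluation for psychiatric worsening, weekly medical evaluation, round-the-clock availability, the 25% HAM-D criterion, and Section 14.1. A reader might infer that a C-SSRS finding cannot lead to withdrawal, or that participants are left unprotected. The documents support neither, because clinicians are free to act on any such finding. What survives is the difference between being required and being allowed to withdraw someone. The protocol chose a mandatory rule for this event and then left out a source that it already collects.

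Finally, merely adding the name of the C-SSRS would set no threshold and would leave the word significant undefined. That objection is sound, and the change below is worded to meet it.

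**Conclusion.** The point holds as a minor gap in the written rule and is best treated as a cheap improvement. Suicidal plan or intent elicited on the C-SSRS or at interview is not itself a mandatory ground for discontinuation during treatment. It becomes one only through item #3 above 3 or a 25% rise in the HAM-D total, and is otherwise left to discretion.

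The conclusion rests on reading the two routes in the first criterion as exhaustive, and on the ordinary meaning of spontaneous, under which an answer to a direct question does not qualify. Confidence is high on the text. The practical size is unknown: the number of participants affected cannot be estimated from the documents, and no claim is made that any would be missed.

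**What to change.** In Section 6.3, Stopping Rules, extend the first criterion after the item #3 route with: *or suicidal plan, intent or behaviour newly reported since Baseline on the C-SSRS or at clinician interview, or a clinician's judgment that the participant is an imminent danger to self or others.* Leave the two existing routes as they are. Elicited ideation without plan or intent would stay under clinician judgment, so that participants who entered with such ideation are not removed for it. The Baseline C-SSRS already provides the reference for what is new.

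The cost is one amended sentence. No visit, scale or rating is added. The downside is possibly a few more discontinuations, each of which uses one of the 5 places between 35 randomized and 30 completers. Some of these participants would probably have been withdrawn under Section 14.1 anyway, so the net loss should be smaller than the number of new triggers.

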7.0 Data and Specimen Banking* N/A

7.1 De-identified plasma samples and buffy coat (collected from 2, 6cc tubes EDTA whole blood at 4 degree) for inflammatory markers and L-DOPA concentrations, and Tempus tubes for mRNA (from ~3-4 cc blood) will be collected in this study at baseline and Weeks 1, 3, 4 and 6. 10mL samples (in EDTA at RT) will also be collected for immune cell extraction. Samples will be stored in the -80-degree freezers (or liquid nitrogen for immune cells) in the Behavioral Immunology Program Laboratory on the 5th Floor of Clinical B at Emory. Samples will be analyzed by the PI and the Laboratory Research Associate or other laboratory personnel that are approved on this protocol, or sent to core laboratories within Emory University for analysis (i.e. the Genomics Core lab, Biomarker Core Laboratory) or elsewhere (see section 17.4).

7.2 Samples will be de-identified and only the study personnel approved on this protocol will have access to the samples or to the data that is associated with the identifier for each sample.

7.3 External investigators may obtain specimens and the associated de-identified clinical data for research purposes only through a Materials Transfer Agreement to be prepared and approved by the Emory Technology Transfer Office and the Emory Office of Sponsored Programs.

8.0 Sharing of Results with Participants*

8.1 The results of screening laboratory tests conducted by EML will become part of each participant's Emory Healthcare medical record and will be shared with them. Other results such as computer tests, medical and psychiatric history, health status updates, questionnaires, urine drug screen results, research lab work for looking at inflammation, and MRI scans are not intended for clinical use and will be kept only in a research record. These results will not be placed in their Emory Healthcare medical record and will not be reported to participants or to other healthcare providers who may be providing them treatment.

The Principal Investigator and research staff may also share PHI or results with the following parties to help conduct the study or to ensure safety or regulatory compliance:

1. Emory offices that are part of the Human Research Participant Protection Program and those that are involved in study administration and billing. These include the Emory IRB, the Emory Research and Healthcare Compliance Offices, and the Emory Office for Clinical Research.
2. Government agencies that regulate the research including: Office for Human Research Protections; Food and Drug Administration.
3. Public health agencies including the sponsor of the study, the National Institute of Mental Health (NIMH).
4. Research monitors and reviewer.
5. Accreditation agencies.

8.2 The fMRI scans that will be completed as data for this study are not designed to detect or diagnose problems of the brain. A radiologist will not be reading the scans. However, it is still possible that we will see something on a structural scan that is potentially abnormal. If this happens, we will discuss it with the participants.

8.3 During the consent process, participants will be informed that they will receive the results of their screening laboratory tests performed by EML. Participants will also be informed that their other results (i.e. computerized testing, psychiatric evaluations, as described above) are not intended to be clinical or diagnostic and will not be reported. They will also be informed that although MRI scans are also not diagnostic, will not be reviewed by a radiologist, and that fMRI results will not be reported, they will be informed that if an abnormality is observed during collection of MRI data, this finding will be discussed with them by the PI, Study Physician or their designee. Participants will have the option to opt out of receiving their lab results or being alerted to any incidental findings.

8.4 This study is not designed to provide treatment and does not include a budget for the diagnosis or treatment of incidental findings uncovered during participation in this research. The study team will discuss the screening laboratory results with the participant, including going over values that are outside of the normal range. Patients with abnormal results will be advised to schedule a visit with their primary care or treating physician. If potential abnormalities are observed during MRI scans, the participants will be informed that a potential structural abnormality was observed and that it

| Table 3: Timeline | Year 1 (R61) | | | | Year 2 (R61) | | | | Year 3 (R33) | | | | Year 4 (R33) | | | | Year 5 (R33) | | | |
|-------------------------------|--------------|----|----|----|--------------|----|----|----|--------------|----|----|----|--------------|----|----|----|--------------|----|----|----|
| | Q1 | Q2 | Q3 | Q4 |
| Start-up & training | X | | | | | | | | X | | | | | | | | | | | |
| Accrual (completers) | | 5 | 10 | 15 | 20 | 25 | 30 | | 5 | 10 | 20 | 25 | 30 | 35 | 40 | 45 | 50 | 55 | 60 | |
| Cytokine/image analysis | | | | X | X | | | | X | | | | | X | | | X | X | X | |
| Gene expression (R61) | | | | | | X | | | | | | | | | | | | | | |
| DSMB report | | | | X | | | X | | | X | | | | | X | | | | | X |
| Annual reports NIH/IRB | | | X | | | | X | | | X | | | | | X | | | | | X |
| Final data cleaning | | | | | X | X | X | | | | X | X | X | X | | | | X | X | X |
| Final analysis | | | | | X | X | | | | | | | X | X | X | | | | X | X |
| Decision on Go/No-Go criteria | | | | | | X | | | | | | | | | | | | | | X |

is recommended that they schedule an appointment with their primary care doctor or a specialist, if applicable.

